#### Other secondary endpoints

- Time to worsening in prostate cancer-related urinary symptoms, defined as an increase from baseline of greater or equal to 8 points in the urinary symptom scale/score (PRURI) measured using the prostate cancer module of the European organisation for research and treatment of cancer (EORTC) quality of life questionnaire (QLQ) (EORTC-QLQ-PR25).
- Time to next symptomatic skeletal event, defined as the time from randomisation until first occurrence of one of the following: a symptomatic fracture, radiation or surgery to bone or a spinal cord compression (PCWG3 criteria).

**Note:** *The occurrence of these events will be determined by investigator evaluation. No systematic X-Ray will be performed.*

- Complete PSA response (defined as PSA  $\leq$  0.2 ng/ml) at 6 months.
- Prostate cancer-specific survival, defined as the time from randomisation to the date of death due to prostate cancer (deaths due to other causes will be censored).
- Time to deterioration for EORTC QLQ-PR25 symptom subscales, defined as the first decline in the HRQoL score from baseline equal to or greater than the minimally important difference (MID; a measure of clinical significance) defined as half the standard deviation of the baseline value for each subscale.
- Time to first subsequent systemic anti-cancer therapy (SACT) defined as the time from randomisation to the date of initiation of any SACT for CRPC, following initiation of the study treatment.
- Efficacy of subsequent SACT will be assessed according to rPFS, OS, and PFS after next line of treatment (PFS2); defined as the time from randomisation to second objective disease progression, or death from any cause, whichever first.
- Health related quality of life will be evaluated using the EORTC-QLQ-C30, EORTC-QLQ-PR25 and BPI-SF questionnaires.
- Geriatric status will be evaluated using the Geriatric Core Dataset (G-Code) assessment.
- Impact of sarcopenia on overall survival will be evaluated by comparing the distribution of overall survival between sarcopenic and non-sarcopenic patients.
- Impact of sarcopenia on treatment response will be evaluated by comparing rate of response in sarcopenic and non-sarcopenic patients.

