#### 7.4. End-of-treatment visit

Patients will continue to receive study treatment and undergo study procedures as outlined above until radiographic disease progression. Study treatment will be continued for subjects who have increasing PSA values in the absence of radiographic or clinical progression. Although serial PSA measurements will be performed in this study, progression or change in PSA values is not considered a reliable measure of disease progression and should not be used as the lone indicator for discontinuation.

In case of clinical progression without radiographic progression, the investigator should also assess whether it is the patient's best interest to stop study treatment and change to another therapy, or in selected cases, to carry on with the study treatment.

Treatment may also be terminated early at the initiative of either the patient or the investigator for any reason that would be beneficial to the patient, including: unacceptable toxicity, intercurrent conditions that preclude continuation of treatment, or patient request.

If the study treatment is terminated, the ADT should be continued.

Following treatment discontinuation for any reason, the following examinations are to be performed 30 ( $\pm$  3) days after last dose of study treatment, or before initiating a new antineoplastic therapy, whichever comes first:

- Complete clinical examination (major body systems).
- Collection of height and body weight.
- Measurement of vital signs (blood pressure, seated heart rate, body temperature).
- Assessment of ECOG performance status.
- Electrocardiogram (only in case of abnormal results at screening visit, or if clinically indicated by patient symptoms)
- Assessment of ongoing toxicities including pre-existing symptoms and any concomitant therapies received.
- Haematology analysis (see Table 3, page 47).
- Serum chemistry (see Table 3, page 47).
- Measurement of serum PSA and testosterone levels.
- Assessment of patient quality of life using the following tools:
  - EORTC-QLQ-C30 (Appendix 10)
  - EORTC-QLQ-PR25 (Appendix 11)
  - BPI-SF (Appendix 12)

- Assessment of patient geriatric status using the G-CODE assessment tool (Appendix 8).
- **For patients who provide additional informed consent:** Where medically feasible a biopsy should be performed at time of disease progression to collect a treatment-resistant tumour sample.

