**Table 5. Censoring rule for primary analysis of radiographic progression-free survival**

Censoring situation	Date of censoring
No baseline assessment	Date of randomisation
No post-baseline assessment and no death prior to first scheduled assessment	Date of randomisation
No radiographic progression or death on study	Date of last tumour assessment
Withdrawn from the study without documented radiographic progression	Date of last tumour assessment

The primary analysis for the rPFS endpoint will be done considering the first radiographic progression observed under study (even if this first radiographic progression is observed under a subsequent line of therapy). As a sensitivity analysis, in case of initiation of a subsequent line of therapy before observing a radiographic progression, the data will be censored at the time of initiation of the salvage treatment.

The final analysis of the primary endpoint will be event-driven, to be performed when at least 197 patients have experienced radiographic progression or death.

Inference for the primary endpoint will be assessed using a two-sided stratified log-rank statistic as the primary analysis. The analysis on stratification factor at randomisation: LATITUDE risk criteria (high risk versus low risk) and ECOG performance status score (0 or 1 vs 2).

A patient is considered as high risk according to the LATITUDE criteria if he has at least two of the three following high-risk factors associated with poor prognosis: a Gleason score of 8 or more (on a scale of 2 to 10, with higher scores indicating more aggressive disease), at least three bone lesions, and the presence of measurable visceral metastasis. He is otherwise considered as low risk ([Fizazi, 2017](#)).

In case the stratification factor does not have sufficient number of patients (less than 3%) and the inferential analyses would be negatively impacted, the stratification factor will not be included as a stratification factor in this analysis.

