The proportional hazard assumption will be assessed graphically by plotting log (-log[estimated survival distribution function]) against log(survival time). The resulting graphs should have approximately parallel lines when the assumption holds. If the proportional hazards assumption is reasonably met, then a stratified Cox proportional hazard model will be used to estimate the treatment effect using Hazards Ratio (HR) and its two-sided 95% confidence interval (95%CI). If the proportional hazards assumption is violated, then the inference remains statistically valid for testing equality in survival distributions. In addition, rPFS will be descriptively summarized using Kaplan-Meier methodology, including medians and two-sided Rothman's 95%CI ([Kaplan, 1958](#); [Rothman, 1978](#)).

Stratification factors will include:

- LATITUDE risk criteria (high risk versus low risk, [Fizazi, 2017](#))
- ECOG performance status score (0 or 1 vs. 2).

If final analysis of the primary endpoint meets the pre-specified hypothesis (see Section 10.1), an additional sensitivity analysis of rPFS will be performed using the results of a centralised disease evaluation by an independent review committee (IRC).

All the other secondary time to event endpoints (namely, CRPC-free survival, clinical progression-free survival, time to worsening in prostate cancer-related urinary symptoms, time to next symptomatic skeletal event, prostate cancer specific survival and overall survival, time to first subsequent SACT and time to second subsequent SACT) will be analysed using the same methods as the primary endpoint (stratified two-sided log-rank test, stratified Cox proportional hazards models). Secondary endpoints will be analysed according to the investigators' assessment of response. Censoring rules for these endpoints will be detailed in the SAP.

The median follow-up will be estimated using the inverse Kaplan-Meier method ([Schemper, 1996](#)).

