### Castration resistance

Castration resistance is defined as serum testosterone being at a castrated level  $\leq 50$  ng/dL (equivalent to 0.50 ng/mL or 1.73 nmol/L), plus either:

- a) Biochemical progression: Two consecutive increases in PSA of at least  $>1$  ng/mL over the nadir, measured at least 1 week apart, (see Figure 3 below).

The date of biochemical progression will be the date where the PSA testing confirms that the progression criteria have been met.

[figure not shown]
OR

- b) Radiographic progression: as per the above definition

The date of castration resistance will be the first date among the date of biochemical progression and the date of radiographic progression.

The appearance of a single new bone lesion in the absence of biological progression will not be considered as castration resistance. Resistance to castration will be characterized by the appearance of a second bone lesion (or a visceral lesion) and / or biological progression. In this case, the date of detection of the second lesion will be the date of resistance as per the above definition.

**Note:** Symptomatic progression should be subject to further investigation before diagnosing CRPC. It is not sufficient alone to diagnose castration resistance.

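### As defined, PFS2 does not record failure of the next line in patients who change therapy before objective progression, and the analysis list does not match the endpoints defined on later therapy

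*Protocol*

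**What the plan says.** - **PFS2.** Section 3.2.2, repeated in the summary, measures the efficacy of subsequent systemic anti-cancer therapy (SACT) by, among others, "PFS after next line of treatment (PFS2); defined as the time from randomisation to second objective disease progression, or death from any cause". The protocol does not define objective disease progression.
- **Time to first subsequent SACT.** The same section runs this from randomisation to "the date of initiation of any SACT for CRPC, following initiation of the study treatment".
- **Change of therapy.** Section 7.4 says: "In case of clinical progression without radiographic progression", the investigator weighs whether to "stop study treatment and change to another therapy". Section 5.6 leaves later therapy to the physician after any discontinuation, including for toxicity.
- **rPFS.** Section 10.3.2 counts the first radiographic progression "even if this first radiographic progression is observed under a subsequent line of therapy". A sensitivity analysis censors such patients when the new therapy starts.
- **Analysis list.** The secondary time-to-event endpoints named in section 10.3.2 include "time to first subsequent SACT and time to second subsequent SACT". PFS2 is not named. For these endpoints the section defers only the censoring rules to the SAP.
- **Castration resistance.** Appendix 3 requires castrate testosterone plus PSA or radiographic progression. Of symptomatic progression it says: "It is not sufficient alone to diagnose castration resistance".
- **Imaging after an early stop.** The summary ends it at progression, a new antineoplastic treatment or death. Sections 7 and 7.5.1 continue it until progression or death and do not mention a new treatment.

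**The concern.** An endpoint named for the next line of treatment should have its event when that line fails. Counting progressions gives this only if progression number one happened on study treatment. The protocol foresees patients for whom it did not, and deals with them for rPFS but not for PFS2.

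The effect on later lines of therapy is a listed secondary objective (section 2.2). PFS2 would be too long for these patients. If they were commoner in one arm, the comparison would be distorted as well. The two SACT points bear on the same objective: one endpoint is listed for analysis without a definition, and another may pass over a real change of therapy.

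**Working it through.** The plan gives no figure for this point, so the definitions are traced through a patient path first. The size is then illustrated with assumed inputs.

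**1. One patient (invented dates).** He has clinical but no radiographic progression at month 8 and changes to therapy B. He progresses radiographically on B at month 14.

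- rPFS (section 10.3.2): event at month 14, on the later line.
- PFS2 as its name suggests: event at month 14, because the next line has failed.
- PFS2 as defined: month 14 is progression number one, so there is no event. If a further line lasts 6 to 9 months, the event falls at month 14 + 6 = 20 to 14 + 9 = 23, or at death if earlier.
- Time to first subsequent SACT: therapy B counts only if it was given for castration-resistant disease. If neither the PSA nor the radiographic criterion of Appendix 3 was met at month 8, it need not count.

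**2. Size per switcher (simulation, all inputs assumed).** Exponential times were used, with medians of 6 or 12 months to progression on the next line, 4 or 8 months on the line after, and 24 or 36 months from switch to death. Median time from switch to event is 4.8 to 9.0 months when the event is next-line progression or death. It is 8.9 to 16.3 months as defined. Within the eight combinations the gap runs from 3.6 months (11.6 − 8.0) to 7.6 months (12.7 − 5.1).

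**3. Size for the whole group (all inputs assumed).** The medians are 12 months to the end of the first stage, 9 on the next line, 6 on the line after, and 36 from randomisation to death. The mean shift can be checked by hand:

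- Probability of reaching next-line progression alive: (1/12)/(1/12 + 1/36) × (1/9)/(1/9 + 1/36) = 0.75 × 0.80 = 0.60.
- Mean extra time until the next progression or death: [1/(1/6 + 1/36)]/ln 2 = 5.143/0.693 = 7.42 months.
- Mean excess per switcher: 0.60 × 7.42 = 4.45 months.

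| Share switching early | Mean shift (share × 4.45) | Simulated median: next-line event → as defined |
|---|---|---|
| 10% | 0.45 months | 16.9 → 17.3 (+0.4) |
| 20% | 0.89 months | 16.8 → 17.7 (+0.9) |
| 30% | 1.34 months | 16.9 → 18.2 (+1.3) |

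If 20% of one arm and 10% of the other switched early, the spurious difference in medians would be about 0.9 − 0.4 = 0.5 months. At 30% against 10% it would be about 1.3 − 0.4 = 0.9 months.

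**4. Section 3.2.2 against section 10.3.2.** PFS2 is defined in the first and absent from the list in the second. Time to second subsequent SACT is in the list and defined nowhere. This mismatch needs no assumption.

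**The case against.** Several points on the other side stand and limit the finding.

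- **Imaging around a switch.** Section 7.3.8 asks for extra imaging when symptoms call for it. Section 7.4.1 requires a disease evaluation around the last dose or before a new therapy, unless a recent one exists. Many clinical progressors will therefore have radiographic progression on record before they switch, and for them name and definition agree. The subgroup is smaller but not empty: section 7.4 describes it, and section 10.3.2 has a sensitivity analysis for it.
- **Eligibility.** Inclusion criterion 6 requires ineligibility for docetaxel, abiraterone, enzalutamide and apalutamide. A switch to another systemic agent while still castration-sensitive is therefore probably uncommon.
- **The word objective.** If PSA progression counted, some switchers would already have their first event. Section 7.4 calls PSA change unreliable as a measure of progression, so the radiographic reading is the natural one. The missing definition is part of the defect.
- **Not every PFS2 is delayed.** Death still ends it, and a second progression can occur on the same line if that therapy continues.
- **SACT for CRPC.** The restriction may be deliberate. PSA and testosterone are measured at every visit from Day 30 and at end of treatment, so many symptomatic switchers will already meet the criteria and be counted. A reader might infer that the endpoint is wrong. The text supports only that a switch without documented castration resistance need not count.
- **Direction.** A reader might infer that the wording lengthens PFS2 mainly on placebo and so hides a benefit. That is plausible for clinical progression, but no switching rate by arm is given. For stops due to adverse events, section 1.4.1 reports similar rates in the earlier placebo-controlled trial (8.9% on darolutamide, 8.7% on placebo).

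**Conclusion.** The point holds for a defined subgroup. For a patient who changes therapy before any objective progression, PFS2 as worded does not end when the next line fails, and it is overstated for him. This rests on reading objective as radiographic. The size of the subgroup and any imbalance between arms are unknown, and the 0.4 to 1.3 month shifts in the overall median are illustrations. If early switches were commoner on placebo, the comparison would be biased against darolutamide. The documents do not establish that they are.

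Section 10.3.7 treats endpoints other than the key secondary ones as exploratory, without adjustment for multiplicity. The primary conclusion is unaffected. It would be wrong to infer that PFS2 fails as a whole or that the trial's main result is at risk.

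The mismatch between sections 3.2.2 and 10.3.2 is a plain inconsistency. All of this is worth correcting, because the event definitions are fixed in the protocol.

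**What to change.** 1. **PFS2 (section 3.2.2 and summary).** Define it as the time from randomisation to the first objective progression (radiographic, by PCWG3) on or after the start of the first subsequent systemic anti-cancer therapy, or death, whether or not radiographic progression preceded that therapy.
2. **Patients who start no further therapy.** State a rule, because under item 1 they can have no event except death. One option is an event at death and otherwise censoring at the last assessment, with the present second-progression definition kept as a sensitivity analysis.
3. **Section 10.3.2.** Add PFS2 to the list, and either define or delete time to second subsequent SACT. Do not assume that one was meant in place of the other.
4. **Time to first subsequent SACT.** Report it for any new systemic anti-cancer therapy for prostate cancer, excluding continued or substituted ADT, alongside the version limited to castration-resistant disease.
5. **Imaging after an early stop.** Reconcile the summary with sections 7 and 7.5.1. The answer decides whether next-line progression in these patients is seen on scheduled imaging or only in routine care.

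The cost is wording in three places, plus the reconciliation in item 5. Section 7.5 already collects start dates of later therapies and progression dates. It limits them largely to what the medical file holds, so completeness after a switch depends on item 5. Items 1 to 4 change no treatment or clinical rule.

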### 3.3. Progression of the trial

Patients participating in the trial will comply with the protocol for an estimated 12 months of treatment and subsequent follow-up for up to 10 years from the date of randomisation.

The end of the study corresponds to the last visit of the last patient.

The investigation/examination schedule is defined by the trial schedule of activities in Section “[Schedule of visits and activities](#)” of the protocol summary.

### 3.4. Inclusion and randomisation procedure

Patients written informed consent is to be obtained before any study related procedures are performed. Candidates who consent to study participation will then enter the Screening period (max. 28 days prior to start of treatment) during which all examinations required to assess their eligibility will be performed, including demographic data collection, tumour evaluation and clinical and laboratory evaluations (see Section 7.1). The availability of a suitable formalin-fixed, paraffin-embedded (FFPE) biopsy sample of a metastatic site or primitive tumour tissue will be verified during the screening period. Blood samples will also be collected prior to the start of treatment.

Eligible patients will be randomised via the interactive web response system (IWRS, <https://ecrf.euraxipharma.fr/csonline/>) and registered on the Unicaner electronic case report form (eCRF, <https://ecrf.icm.unicancer.fr/csonline/>) with a unique identification number. This number must be used as the sole patient identifier throughout the study.

It is the responsibility of the investigator to verify and confirm that all inclusion and non-inclusion criteria are met prior to randomisation.

Eligible patients will be randomised (1:1) via a specific Interactive Web Response System (IWRS) to receive either:

- Experimental arm: ADT + darolutamide 600 mg po b.i.d.
- Control arm: ADT + placebo po b.i.d.

Randomisation will be blinded, and stratified according to LATITUDE risk criteria (high risk versus low risk) and ECOG performance status score (0 or 1 vs. 2) using a system of different sized random permuted blocks to ensure the treatment arms are balanced for all combinations of stratification factors. A patient is considered as high risk according to the LATITUDE criteria if he has at least two of the three following high-risk factors associated with poor prognosis: a Gleason score of 8 or more (on a scale of 2 to 10, with higher scores indicating more aggressive disease), at least three bone lesions, and the presence of measurable visceral metastasis. He is otherwise considered as low risk ([Fizazi, 2017](#)).

E-mail confirmation of the randomisation and assigned treatment number will be sent to the Investigator, Statistician, Sponsor and Data Manager.

Instructions for the use of the IWRS will be provided to all investigators during the trial initiation visit at each site.

### **3.5. Procedure for breaking the randomisation code (unblinding)**

Except in case of necessity to implement an immediate treatment for a serious adverse event (SAE), breaking the randomisation code may be authorised only in case of absolute necessity (in instances when the nature of the treatment allocated is necessary for patient management) or after approval from the sponsor.

Unblinding is performed via the IWRS. Instructions for the use of the IWRS will be provided to all investigators during the trial initiation visit at each site.

### **3.6. Premature Trial Terminations and Suspension**

The trial may be suspended or stopped by the sponsor after meeting with the coordinating investigators or following a request by the respective regulatory authority and/or the responsible Ethics Committee for the following reasons:

- High frequency and/or unexpected severity of toxicity
- Insufficient patient enrolment
- Lack of significant results («futility»)
- Insufficient quality of data collection

### **3.7. Patient's trial withdrawal and discontinuation**

Patient withdrawal concerns patients who stop treatment and all other protocol-defined procedures. Please note that treatment discontinuation without consent withdrawal from a patient is not

considered as a trial withdrawal. For treatment discontinuation only, please refer to Section 5.6. This can occur under the following circumstances:

- Patient withdraws consent
- The principal investigator may terminate a patient's participants from the trial, if this is in the interest of the patient.

Trial patients may withdraw their consent at any time without justification, irrespective of the reason(s). In the case of withdrawal, the investigator should attempt to obtain as much information as possible. This information should be noted in the patient's medical file. The patient's withdrawal of consent does not impact the patient's right to receive medical treatment.

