## 5.6. Patients' discontinuations of treatment

Patients can discontinue the trial treatment for the following reasons:

- Unacceptable toxicity.
- Patients decline further treatment/therapy but accept to continue with protocol.
- Investigator's decision.

- Radiographic disease progression

After discontinuation of trial treatment, subsequent therapy decisions are left to the physician's discretion.

Patients who discontinue trial treatment will continue with the trial and the protocol-defined procedures, unless they specifically withdraw their consent and indicate that they do not want to perform any further trial-related visits or assessments (for patient withdrawals see Section 3.7).

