## 6. EVALUATION OF TREATMENT EFFICACY AND SAFETY

### 6.1. Efficacy evaluation

Treatment efficacy will be evaluated by measuring changes in tumour size/number of lesions (see Section 7.3.8) and serum PSA levels in response to treatment; according to PCWG3 criteria ([Scher, 2016](#); Appendix 3).

Patient's disease will be assessed at "baseline" (during the screening period) and then every 120 (±14) days after randomisation during the first 2 years and every 180 (±14) days thereafter, until documented radiographic progression, or death, whichever occurs first. For patients who discontinue study treatment for reasons other than radiographic progression, death, or consent withdrawal, investigators will continue to perform disease evaluations during the follow-up period until progression.

The primary evaluation endpoint is radiographic progression-free survival, defined as time from randomisation to radiographic progression according to PCWG3 criteria or death, whichever occurs first.

For secondary evaluation endpoints see Section 3.2.2.

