### 7.5. Follow-up

Long-term follow-up assessments will be performed for all patients every 180 ( $\pm$  14) days following the EoT visit.

The following information will be collected at each LTFU assessment:

- Patients survival status.
- Subsequent antineoplastic therapies (including regimen administered [drug, dose, frequency, mode], start and stop dates).
- Efficacy data (including response to subsequent antineoplastic therapies, dates of progression and evaluation of serum PSA levels).
- Status of ongoing AEs and/or new treatment-related AEs.

No study specific evaluations will be performed during the LTFU period, other than those described in Section 7.5.1 below. Data collection will be limited to that information which is available in the patient's medical file and evaluations performed as part of patients continued treatment at the site, or obtained via communication with the patients treating physician or via telephone contact with the patient.

Long-term follow-up will continue until death, withdrawal of consent, or 10 years after date of patient randomisation, whichever occurs first.

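### Section 3.7 lets the investigator end a patient's whole trial participation without withdrawal of consent, against sections 5.6, 6.1, 7.5 and 7.5.1, and Table 5 then censors that patient for rPFS

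*Protocol*

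**What the plan says.** Section 3.7 of the protocol opens with a broad definition: "Patient withdrawal concerns patients who stop treatment and all other protocol-defined procedures". It sends patients who only stop treatment to section 5.6. It then gives two circumstances for withdrawal. One is that the patient withdraws consent. The other is "The principal investigator may terminate a patient's participants from the trial, if this is in the interest of the patient".

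Other sections describe follow-up differently:

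- Section 5.6 lists "Investigator's decision" among the reasons for stopping treatment, and adds "Patients who discontinue trial treatment will continue with the trial and the protocol-defined procedures, unless they specifically withdraw their consent".
- Section 6.1 covers patients who stop treatment for reasons other than radiographic progression, death or consent withdrawal. For them, "investigators will continue to perform disease evaluations during the follow-up period until progression". Section 7.5.1 repeats this for the long-term follow-up period.
- Section 7.5: "Long-term follow-up will continue until death, withdrawal of consent, or 10 years after date of patient randomisation, whichever occurs first". It allows the information to come from the medical file, the treating physician or a telephone call.

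On the analysis side, Table 5 in section 10.3.2 is titled "Censoring rule for primary analysis of radiographic progression-free survival". Its fourth row, "Withdrawn from the study without documented radiographic progression", censors at the date of the last tumour assessment. The overall survival rule stands separately in section 3.2.2. It censors subjects alive at the analysis and names loss to follow-up and withdrawal of consent.

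**The concern.** A site that follows 3.7 may stop scans and survival contact for a patient who has refused neither. Sections 5.6, 6.1, 7.5 and 7.5.1 tell the same site to continue. With up to 100 sites, both readings can be applied in one trial.

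The primary endpoint counts death from any cause, and section 10.2 analyses all randomised patients. Row 4 of Table 5 does not ask who initiated the withdrawal. A patient removed by the investigator is therefore censored at his last scan even if his later death is known. Every patient is frail by eligibility, so removal in the patient's interest may well be related to his prognosis. Censoring related to prognosis can bias the hazard ratio, and the bias need not be equal in the two arms.

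**Working it through.** **1. The passages side by side**

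| Situation | 3.7 | 5.6, 6.1, 7.5.1 | 7.5 | Table 5 (rPFS) |
|---|---|---|---|---|
| Investigator stops treatment only | Not a withdrawal; see 5.6 | Stays in trial; imaging to progression or death | Survival follow-up continues | Event counts |
| Patient withdraws consent | Withdrawal | Exit allowed | Exit allowed | Row 4: last tumour assessment |
| Investigator ends participation, consent not withdrawn | Withdrawal; all procedures stop | No such exit | No such exit | Row 4: last tumour assessment |

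The third line is the conflict. A patient in that position has also stopped treatment, so 5.6 applies to him and keeps him in the trial. Row 3 of Table 5 does not help, because it refers to progression or death *on study* without saying whether a removed patient is still on study.

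**2. The plan's own figures reproduce**

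Inputs from section 10.1: HR 0.65, two-sided alpha 0.05, power 85%, medians 12 and 18.5 months, drop-out hazard 0.014 (taken as per month), accrual of 18, 50, 53 and 179 patients over months 0–12, 12–24, 24–36 and 36–60, and a cut at month 75.

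- Events by Schoenfeld: 4 × (1.960 + 1.036)² / (ln 0.65)² = 194. By Freedman: (1.960 + 1.036)² × (1.65/0.35)² = 200. The stated 197 lies between them, with power 85.6% (fixed design).
- With event hazard h, drop-out hazard d and follow-up f, the event probability is h/(h+d) × (1 − e^(−(h+d)f)). Averaged over accrual, with h = ln2/12 = 0.0578 (control), 0.65 × 0.0578 = 0.0375 (experimental) and d = 0.014, this gives 107.8 + 88.9 = 196.7 events.
- Drop-outs, with d in the numerator, are 26.1 + 33.1, about 59 or 19.8%, against the stated maximum of 19.3%.
- With d = 0 the expected events are 234.3. So 234.3 − 196.7, about 38 events, would fall after drop-out and before month 75.

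The 197 is therefore already net of the planned drop-out. The calculation treats drop-out as a constant hazard, equal in both arms and unrelated to the event. It covers lost power under those conditions. It gives no protection if removal depends on prognosis.

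**3. What informative removal could do (illustration only)**

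Assume a fraction f of would-be rPFS events is censored just before it occurs. The observed hazard is then (1 − f)h, and the apparent HR is 0.65 × (1 − f_exp)/(1 − f_ctl).

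| f control | f experimental | Events lost by month 75 | Apparent HR (true 0.65) | Apparent HR (true 1) |
|---|---|---|---|---|
| 5% | 5% | 9.8 | 0.65 | 1.00 |
| 10% | 10% | 19.7 | 0.65 | 1.00 |
| 10% | 5% | 15.2 | 0.69 | 1.06 |
| 5% | 10% | 14.3 | 0.62 | 0.95 |

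Equal losses leave the HR alone. They would lower power at month 75 from 85.6% to 83.7% (5%) or 81.7% (10%). The final analysis waits for 197 events, so in practice the price would be time. Unequal losses move the estimate in either direction. For scale, 14 to 15 lost events is about a quarter of the 59 planned drop-outs, each removed just before an event, which is a severe assumption. The protocol supports none of these fractions.

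**The case against.** The best defence is that a site would have to put one general sentence ahead of several operational ones. Toxicity and investigator decision are already treatment-stopping reasons in 5.6, clinical progression without radiographic progression is handled in 7.4, and imaging and survival follow-up then continue. Section 3.7 also asks the investigator to obtain as much information as possible at withdrawal. And drop-out is in the sample size, with an event-driven final analysis. This makes a large loss unlikely and removes any claim of a shortfall against 197 events. It does not remove the conflict: 3.7 says *from the trial*, its request for information does not require scans or survival status to continue, and row 4 censors whatever is later learned.

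Four stronger readings are tempting but not supported:

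- **Table 5 also costs survival events.** It governs rPFS only. Under section 3.2.2 a known death counts for overall survival, whoever ended participation.
- **Those removed are mostly declining patients.** The protocol says only that removal is in the patient's interest. It gives no reasons, rate or arm difference.
- **A number of lost events can be read off.** If a quarter to a half of the 38 post-drop-out events were put down to investigators, the result would be 9 to 19. That share has no source, the drop-out allowance also includes non-evaluable patients, and progression that needs CT or MRI and bone scan cannot all be recovered.
- **Section 3.7 contradicts its own note.** The note concerns stopping treatment alone, which is a different case.

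**Conclusion.** The point holds as a conflict in the text that reaches the primary analysis. Section 3.7 creates an exit from the trial that 5.6, 6.1, 7.5 and 7.5.1 do not recognise. Row 4 of Table 5 turns that exit into censoring at the last scan, even when a death is known.

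That this censoring is informative is a plausible inference, not a documented fact. Its size and direction cannot be given, because the protocol states no rate of investigator termination. The hazard ratios of 0.62 to 0.69 show only what uneven losses of 5% and 10% would do under the stated assumption. The planned 197 events and 85% power are not in question. Overall survival is affected only if a site, relying on 3.7, stops collecting survival status. The passages should be reconciled; about 115 of 300 patients were enrolled at this amendment, so most of any loss is still preventable.

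**What to change.** **Section 3.7.** State that an investigator's decision ends study treatment only and is handled under 5.6. Disease evaluation under 7.5.1 and survival follow-up under 7.5 (medical file, treating physician or telephone) then continue unless the patient withdraws consent to them. The grounds for stopping treatment stay as they are.

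**Table 5.** Limit row 4 to withdrawal of consent to further follow-up. Replace *on study* in row 3, so that documented progressions and known deaths in all other randomised patients count as rPFS events. Changing row 4 alone would leave row 3 open to the same reading.

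**Alternative.** If the sponsor wishes to keep the investigator's exit, it should be named in 5.6, 7.5, Table 5 and the overall survival rule, with a sensitivity analysis for those patients. This removes the contradiction but keeps the censoring.

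**Cost.** The preferred fix needs wording changes in one section and two table rows, and no new procedure, since 7.5 already permits remote collection. It means small extra site work for a few patients. Remote follow-up will recover deaths more reliably than radiographic progressions.
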